## **6.6. Exploratory Analysis of Immunogenicity**

The below exploratory analyses of immunogenicity may be performed for Part A and B:

- The genetic and/or phenotypic relationships of isolated SARS-CoV-2 strains to the vaccine sequence.
- Descriptive summaries of clinical profile and immunologic endpoints to characterize participants with SARS-CoV-2 infection during the study.
- Descriptive summaries of GM and GMFR of bAb levels against SARS-CoV-2 nucleocapsid protein (quantitative IgG) and % of participants with 2x, 3x and 4x rise of bAb relative to baseline)
- The magnitude, phenotype, and percentage of cytokine-producing S protein-specific T cells will be summarized at each timepoint by participant group.
- The magnitude and phenotype of S protein-specific B cells relative to baseline will be summarized at each timepoint by participant group.
- Summaries of B-cell receptor sequence analysis to identify representative B-cell clones and determine major antigenic sites & amino acid residues on the SARS-CoV-2 S protein.

Confidential

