
 To describe changes in immunosuppressant medications in SOT recipients after vaccination with mRNA-1273 vaccine 	
 Change in immunosuppressant medications to treat organ transplant rejection or to improve immune tolerance from Day 1 and throughout the study period. Change in immunosuppressant medication is defined as any of the following: 
 any adjustments (temporarily or permanently) in immunosuppressants, addition of new immunosuppressants, or switching from 1 maintenance rejection prophylaxis regimen to another.
Exploratory Objectives	Exploratory Endpoints

 To evaluate the genetic and/or phenotypic relationships of 	
 Comparison of genetic sequence of viral isolates with that of the vaccine sequence

Objectives	Endpoints
isolated SARS-CoV-2 strains to the vaccine sequence	

 To characterize the clinical profile and immune responses of participants with COVID-19 or with SARS-CoV-2 infection 	
 Description of clinical severity and immune responses of participants who are identified as infected by SARS-CoV-2 or having COVID-19

 To describe the incidence of asymptomatic SARS-CoV-2 infection after mRNA-1273 vaccination in adult SOT recipients and healthy adult participants with serologic evidence of infection at baseline 	
 GM and GMFR of bAb levels against SARS-CoV-2 nucleocapsid protein (quantitative immunoglobulin G [IgG]) and percent of study participants with 2\times, 3\times, and 4\times rise of bAb relative to baseline

 To assess, in a subset of SOT recipients who received 3-dose regimen and healthy participants who received 2-dose regimen, SARS-CoV-2 S protein-specific T-cell responses 	
 Magnitude, phenotype, and percentage of cytokine producing S protein-specific T-cells as measured by flow cytometry at Day 1, Day 36, and Day 92 for unvaccinated SOT recipients, at Day 1 and Day 8 for previously vaccinated SOT recipients, and at Day 1 and Day 36 in healthy participants

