8.2. Analyses Sets

The analysis sets are defined in [Table 5](#).

Table 5: Analysis Sets

Analysis Set	Description
Full Analysis Set (FAS)	All participants who received at least 1 dose of vaccine.
Modified Intent-to-Treat Set (mITT)	All participants who have negative SARS-CoV-2 status at baseline, defined as who have a negative RT-PCR test for SARS-CoV-2 and a negative serology test based on bAb specific to SARS-CoV-2 nucleocapsid protein (as measured by Roche Elecsys Anti-SARS-CoV-2 assay) at baseline.
PP Subset	All participants in the mITT set who receive all planned doses of study vaccination per schedule and have no major protocol deviations that impact key or critical data.
PP Immunogenicity Subset	All participants who received planned doses of study vaccination per schedule, complied with immunogenicity testing schedule, and have no major protocol deviations that impact key or critical data. Participants who are seropositive at baseline will be excluded from the PP Immunogenicity Subset. The PP Immunogenicity Subset will be used for analyses of immunogenicity unless specified otherwise. The PP Immunogenicity Set will serve as the primary population for the analysis of SARS-CoV-2-specific bAb and nAb immunogenicity data.
Solicited Safety Set	All participants in the FAS who contributed any solicited AR data. The Solicited Safety Set will be used for the analyses of solicited ARs.
Safety Set	All participants who receive at least 1 dose of vaccine. The Safety Set will be used for all analyses of safety except for the solicited ARs.

Abbreviations: AR = adverse reaction; bAb = binding antibody; nAb = neutralizing antibody; RT-PCR = reverse transcriptase polymerase chain reaction; SARS-CoV-2 = Severe Acute Respiratory Syndrome coronavirus 2; vaccine = investigational product.

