## **2.3. Exploratory Objectives**

The exploratory objectives for Part A are the following:

- To evaluate the genetic and/or phenotypic relationships of isolated SARS-CoV-2 strains to the vaccine sequence
- To characterize the clinical profile and immune responses of participants with COVID-19 or with SARS-CoV-2 infection
- To describe the incidence of asymptomatic SARS-CoV-2 infection after mRNA-1273 vaccination in adult SOT recipients and healthy adult participants with serologic evidence of infection at baseline
- To assess, in a subset of SOT recipients who received 3-dose regimen and healthy participants who received 2-dose regimen, SARS-CoV-2 S protein-specific T cell responses

- To define, in a subset of SOT recipients who received 3-dose regimen and healthy participants, the epitopes recognized by B cells and antibodies generated in response to mRNA-1273

The exploratory objectives for Part B are the following:

- To evaluate the persistence of the immune response of the BD of mRNA-1273 vaccine (100 µg) as assessed by the level of SARS-CoV-2 S2P specific bAb through 6 months after BD
- To evaluate the persistence of the immune response of the BD of mRNA-1273 vaccine (100 µg) as assessed by the level of nAb through 6 months after BD
- To describe the incidence of asymptomatic SARS-CoV-2 infection after mRNA-1273 vaccination in adult SOT recipients and healthy adult participants with negative SARS-CoV-2 at baseline
- To describe the incidence of COVID-19 after vaccination with mRNA-1273 in SOT recipients and healthy participants
- To describe changes in liver and renal function through laboratory tests over time in SOT recipients after vaccination with mRNA-1273 vaccine
- To describe changes in immunosuppressant medications in SOT recipients after vaccination with mRNA-1273 vaccine
- To evaluate the genetic and/or phenotypic relationships of isolated SARS-CoV-2 strains to the vaccine sequence
- To characterize the clinical profile and immune responses of participants with COVID-19 or with SARS-CoV-2 infection
- To describe the incidence of asymptomatic SARS-CoV-2 infection after mRNA-1273 vaccination in adult SOT recipients and healthy adult participants with serologic evidence of infection at baseline
- To assess, in a subset of SOT recipients and healthy participants who received BD, SARS-CoV-2 S protein-specific T-cell responses

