### **6.4. Immunogenicity Analysis**

Immunogenicity samples will be collected at baseline and post-baseline visits, as described in the Schedule of Events in Appendix 1 of Protocol Amendment 4. The PP Immunogenicity Set (Part A/Part B) is the primary analysis population used in the immunogenicity analyses, unless otherwise specified. The mITT set (Part A/Part B) will be used for sensitivity analyses. Concomitant medications and/or vaccines received during the study as described in Section 5.5.3 in Protocol Amendment 4 and Protocol Clarification Memorandum 11 as well as antiretroviral treatments that impact neutralizing antibody responses may be used to determine subject's immunogenicity samples that are eligible for the immunogenicity analyses. Participants will be summarized according to participant group as defined in [Section 6.1](#).

Confidential

The GM levels will be calculated using the following formula:

$$10^{\left\{ \frac{\sum_{i=1}^n \log_{10}(t_i)}{n} \right\}}$$

where  $t_1, t_2, \dots, t_n$  are  $n$  observed immunogenicity levels.

The GMFR measures the changes in immunogenicity levels within subjects. The GMFR will be calculated using the following formula:

$$10^{\left\{ \frac{\sum_{i=1}^n \log_{10}\left(\frac{v_{ij}}{v_{ik}}\right)}{n} \right\}} = 10^{\left\{ \frac{\sum_{i=1}^n \log_{10}(v_{ij}) - \log_{10}(v_{ik})}{n} \right\}}$$

where, for  $n$  subjects,  $v_{ij}$  and  $v_{ik}$  are observed immunogenicity levels for subject  $i$  at time points  $j$  and  $k$ ,  $j \neq k$

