## **6.5. COVID-19 and SARS-CoV-2 Infection Analysis**

For both Part A and Part B, the mITT Set (Part A/Part B) will be used for the analysis of COVID-19 and SARS-CoV-2 infection starting from 14 days after the second dose and third dose received for each participant group. The PP Set (Part A/Part B) may be used in the analyses as appropriate, unless otherwise specified.

**Baseline SARS-CoV-2 status and Pre-booster SARS-CoV-2 Status** is described in [Section 6.1](#). The serology test results based on Roche Elecsys assay at baseline, and the RT-PCR test results at baseline will be summarized by participant group.

Participants with pre-vaccination baseline positive or missing SARS-CoV-2 status will be excluded from the mITT Set (Part A) infection analysis.

Participants with pre-booster positive or missing SARS-CoV-2 status will be excluded from the mITT Set (Part B) infection analysis.

The post-baseline serology test results based on the Roche Elecsys assay and the RT-PCR test results will also be summarized by visit.

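### By default, the nucleocapsid fold-rise summary in SAP 6.6 contains none of the seropositive participants its objective is about

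*SAP*

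**What the plan says.** - **Objective.** SAP 2.3 sets, for Part A and Part B, an exploratory objective on asymptomatic infection in "SOT recipients and healthy adult participants with serologic evidence of infection at baseline".
- **Endpoint.** Protocol Section 2, Table 1 pairs that objective with "GM and GMFR of bAb levels against SARS-CoV-2 nucleocapsid protein (quantitative immunoglobulin G [IgG"]) and the percentage of participants with 2x, 3x and 4x rises. SAP 3.3 repeats the pairing for Part B.
- **Analysis.** SAP 6.6 opens with "The below exploratory analyses of immunogenicity may be performed for Part A and B" and includes "Descriptive summaries of GM and GMFR of bAb levels against SARS-CoV-2 nucleocapsid protein (quantitative IgG"). It names no analysis set and does not restrict the summary to seropositive participants.
- **Default for immunogenicity.** SAP 6.4: "The PP Immunogenicity Set (Part A/Part B) is the primary analysis population used in the immunogenicity analyses, unless otherwise specified". mITT is the sensitivity set. Protocol 8.2, Table 5 says: "Participants who are seropositive at baseline will be excluded from the PP Immunogenicity Subset".
- **Default for infection.** SAP 6.5 uses mITT, with PP where appropriate, and adds: "Participants with pre-vaccination baseline positive or missing SARS-CoV-2 status will be excluded from the mITT Set (Part A) infection analysis". A parallel sentence covers pre-booster status in Part B.
- **Subgroups.** SAP 6.1 offers a split by baseline SARS-CoV-2 status, but marks it as being for safety data.

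**The concern.** A participant who is already nucleocapsid-positive cannot seroconvert, so the plan rightly turns to a quantitative rise for this group. That works only if the group is in the table. The written default rules remove it. A fold-rise table produced under them would describe baseline-negative people, for whom Roche seroconversion is already an endpoint, and would be silent on the people named in the objective.

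The samples are collected in any case. After the last scheduled swab (Day 57, Day 113 or Day 29 in Part A by regimen; the pre-dose BD-Day 1 swab in Part B), a rise in nucleocapsid antibody is the only scheduled means of detecting asymptomatic reinfection in someone already positive. Blood for it runs to Day 394, Day 450 or Day 365, and to BD-Day 181.

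**Working it through.** The plan gives no sample size, power or precision figure for this endpoint, so there is nothing to reproduce. The check is one of set membership.

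**Step 1. Target group.** Participants with positive nucleocapsid serology before the first study dose (Part A) or before the booster (Part B).

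**Step 2. Does the target group overlap each candidate set?**

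| Candidate set | Membership rule | Target group included |
|---|---|---|
| mITT, Part A and Part B (SAP 5.2.1, 5.3.1) | Negative RT-PCR and negative Roche Elecsys nucleocapsid antibody at baseline or pre-booster | 0 |
| PP Immunogenicity, Part A and Part B (SAP 5.2.3, 5.3.3) | Drawn from mITT; Group B4 must also be in mITT (Part B) | 0 |
| PP, Part A and Part B (SAP 5.2.2, 5.3.2) | Drawn from mITT | 0 |
| Full Analysis/Safety Set (SAP 5.1) | At least one dose in the part | All, but assigned to safety |
| Solicited Safety Sets (SAP 5.4) | Safety Set with diary data | Those with diary data, but assigned to solicited reactions |
| mITT-1 (named in SAP 5) | Never defined or assigned | Cannot be determined |

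Every set that a default rule could assign to this summary gives zero. Only sets reserved for safety keep the group.

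**Step 3. Is the target group likely to be empty?** No. Protocol 3.1 lets nucleocapsid-positive participants continue. Known prior infection is an exclusion at Part A entry, so entrants who are positive would be undiagnosed cases. For Part B, Protocol 4.2.2 states exclusion criteria for Group B4 only, and Table 10, footnote 1 allows a booster during the Convalescent Period once symptoms have gone. People infected in Part A can therefore enter Part B. SAP 6.1 counts them as pre-booster positive if any RT-PCR or serology result was positive on or before the booster date.

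**Step 4. Size.** No seropositive fraction is given, so it is assumed. Number at entry = fraction x 240 (220 transplant recipients plus 20 healthy adults, since the objective covers both):

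- 1%: 0.01 x 240 = 2.4
- 5%: 0.05 x 240 = 12
- 10%: 0.10 x 240 = 24
- 15%: 0.15 x 240 = 36

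Even at 1%, the chance of at least one such participant is 1 - 0.99^240 = 0.91. The number captured by the default sets is 0 at every assumed fraction.

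**Step 5. Which assay defines positivity?** The sets use Roche Elecsys; the quantitative IgG comes from the MSD multiplex (SAP Appendix G). Someone Elecsys-negative with measurable MSD IgG could stay in the default sets, but is baseline-negative under the plan's own definition.

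**The case against.** The strongest reply is that the exclusion is inferred. SAP 6.4 applies unless another population is specified, and the objective itself names one. It is also arguable whether SAP 6.4 governs nucleocapsid antibody at all: Protocol 7.2 and SAP 6.4.1 list only neutralizing and spike-binding antibody, and the schedules label nucleocapsid as a nonvaccine antigen. Part of this stands: the zero arises from default rules, not from a sentence about this endpoint. But SAP 6.6 is headed as immunogenicity and Appendix G lists nucleocapsid among the immunogenicity assays. If the summary is treated as an infection analysis instead, SAP 6.5 also leads to mITT. No written rule leads to the seropositive group.

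Two stronger readings are tempting and are not supported.

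- **A reader might infer that no endpoint measures reinfection in previously infected participants.** Protocol 7.3.1 and 7.5.4 record every confirmed COVID-19 case as a medically attended adverse event. These are tabulated in the Safety Set, which keeps seropositive participants, and the baseline-status subgroup applies to safety data. Protocol 8.3.4 also plans counts of symptomatic and asymptomatic infection throughout the study without naming a set. The gap is asymptomatic reinfection, for which the SAP definition (6.5.1.2) is limited to baseline-negative participants.
- **A reader might infer that the Part B table would show Part A infections as rises after the booster**, because the default baseline precedes the first study dose (SAP 6.1) and SAP 6.4.3 takes fold rise from Day 1. Under the default sets, pre-booster positives are already excluded, so most such people would not be in the table. For Group B4 the first study injection is the booster, so the baseline is already right. The problem appears mainly once the population is corrected, which is why the baseline should be settled in the same sentence.

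**Conclusion.** The point holds. Read with its defaults, SAP 6.6 yields a summary with none of the participants the paired objective names, in either part. This follows from the set definitions and does not depend on any assumed seroprevalence.

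Its reach is limited. The objective is exploratory, the analysis is optional, and no primary or secondary conclusion changes. The loss is asymptomatic reinfection in seropositive participants. About 2-36 people at entry is an illustration under an assumed 1-15% of 240; neither end has a source in the documents. Part A infections that go on to Part B would add to it by a number that cannot be estimated from the documents. It is still worth correcting before database lock, because a written rule selects the wrong people and the repair is nearly free.

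**What to change.** Add to SAP 6.6 that, if produced, the nucleocapsid GM, GMFR and 2x/3x/4x-rise summaries use Safety Set participants who have a baseline and a post-baseline nucleocapsid result and who:

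- for Part A, have positive Roche Elecsys nucleocapsid serology at Day 1, with rise relative to Day 1;
- for Part B, have positive Roche Elecsys nucleocapsid serology on or before BD-Day 1, with rise relative to the pre-booster BD-Day 1 sample and not Day 1.

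The criterion should be positive serology, not positive SARS-CoV-2 status. SAP 6.1 counts a positive RT-PCR alone as positive status, and a later rise in a PCR-positive, seronegative person may simply reflect the infection present at baseline. Show those participants, and any baseline-negative summary, separately.

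The cost is a short addition to the SAP and a population flag; the samples and the MSD assay are already planned. The downside is small, purely descriptive denominators, so the number analysed should accompany each estimate.

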## **6.7. Interim Analysis**

An interim analysis of safety and immunogenicity data is planned after Day 57 (28 days after the second study dose for unvaccinated participants) in Part A, after Day 29 (28 days after dose 3 in previously vaccinated SOT recipients) in Part A, and at BD-Day 29 (28 days after BD in participants who receive a BD) in Part B; a clinical study report will be prepared.

## **6.8. Data Safety Monitoring Board**

No Data Safety Monitoring Board is used for this study. A Safety Review Committee (SRC), composed of a transplant nephrologist and hepatologist who are not involved in the conduct of the study, will monitor and adjudicate individual events of transplant rejection. This SRC is described in Section 7.6.1 of Protocol Amendment 4.

## **7. Changes from Planned Analyses in Protocol**

Not applicable.

## 9. List of Appendices

### 9.1. Appendix A. Standards for Safety and Immunogenicity Variable Display in TFLs

**Continuous Variables:** The precision for continuous variables will be based on the precision of the data itself. The mean and median will be presented to one decimal place more than the original results; the SD will be presented to two decimal places more than the original results; the minimum and maximum will be presented to the same precision as the original results.

**Categorical Variables:** Percentages will be presented to 1 decimal place.

### 9.2. Appendix B. Analysis Visit Windows for Safety and Immunogenicity Analysis

Safety and immunogenicity analysis will be summarized using the following analysis visit window for post-injection assessments:

Step 1: If the safety and immunogenicity assessments are collected at scheduled visit, i.e. nominal scheduled visit, the data collected at scheduled visit will be used.

Step 2: If the safety and immunogenicity assessments are not collected at the scheduled visit, assessments collected at unscheduled visit will be used using the analysis visit windows described in [Table 3](#) below.

If a subject has multiple assessments within the same analysis visit, the following rule will be used:

- If multiple assessments occur within a given analysis visit, the assessment closest to the target study day will be used.
- If there are 2 or more assessments equal distance to the target study day, the last assessment will be used.

